9.3 Definition clinical relapse (Cl-Rel)

Clinical relapse is considered as the occurrence of any of the following event in a patient who had showed a hematological response (CR or PR):

- meeting again the criteria for SAA
- requirement of transfusion support (if not due to independent medical conditions)
- decrease in any of the peripheral blood counts as follows
 - Decrease to less than 50% of the medium sustained count during remission if:
 - absolute neutrophils $< 1.0 \times 10^9/L$
 - platelets $< 50 \times 10^9/L$

Or

- In any case if:
 - absolute neutrophils $< 0.5 \times 10^9/L$
 - platelets $< 20 \times 10^9/L$

To qualify a relapse peripheral blood count decrease has to be

- not due to any independent concomitant medical condition
- demonstrated for a minimum of 3 determination over a period of 2 weeks
- not responding to re-introduction of low dose cyclosporin A

9.4 Definition of treatment failure

Any of following events are considered as treatment failure:

- No response at 6 months from treatment starting
- Clinical relapse
- Requirement of further (in addition to ATGAM and CyA) immunosuppressive treatment to sustain response, anytime

9.5 Definition of clonal evolution

Standard karyotype and FISH for chromosomes 7, 8 and 5 will be performed at 3, 6, 12, 18 and 24 months.

Clonal evolution is defined as any of the following [30]:

- Diagnosis of acute leukemia
- Diagnosis of MDS, according to established criteria (by morphology, flow cytometry and karyotype) as defined by WHO 2008 criteria [30]. *The demonstration of a cytogenetic abnormality by itself does not qualify for the diagnosis of MDS, provided that it is not included in the list in Appendix 1*
- Occurrence of any cytogenetic abnormality (in absence of other criteria qualifying for the diagnosis of MDS) which can be demonstrated in at least 10% of bone marrow cells in at least two bone marrow specimens drawn with an interval of at least 3 months.

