6.2 Exclusion Criteria

Patients with one or more of the following criteria cannot be included in the study:

1. Prior immunosuppressive therapy with ATG (horse or rabbit) or any other lymphocyte depleting agent (i.e., alemtuzumab)
2. Eligibility to a sibling allogeneic stem cell transplantation
3. Evidence of a myelodysplastic syndrome, defined by the presence of myelodysplastic features, excess of blasts or karyotypic abnormalities typical of MDS (according to revised WHO 2008 criteria) [30], as well as other primitive marrow disease. Patients with diagnosis of AA with cytogenetic abnormalities which are recurrent in MDS (according to revised WHO 2008 criteria) [30] should be included in this category, and are not eligible for the study; ***patients with del(20q), +8 and -Y are not included in this category, and thus are eligible for this study.*** The list of karyotypic abnormalities which qualifies for the diagnosis of MDS are listed in the Appendix 1.
4. History or clinical suspicion of constitutional aplastic anemia (i.e. Fanconi Anemia with positive DEB/MMC test or Dyskeratosis Congenita)
5. History of malignant tumors with active disease within 5 years from enrollment, and/or previous chemo-radiotherapy
6. Previous history of stem cell transplantation

¹Children in Care (CiC) are not excluded from this study, provided that the agency, organization, institution (or entity of the courts, the government or a government body) will work as legal guardian in signing the informed consent. CiC are defined as children who have been placed under the control or protection of an agency, organisation, institution or entity by the courts, the government or a government body, acting in accordance with powers conferred on them by law or regulation. The definition of CiC can include children cared for by foster parents or living in a care home or institution, provided that the arrangement falls within the definition above. The definition of a CiC does not include a child who is adopted or has an appointed legal guardian.

7. Treatment with cyclosporin A:
 - <4 weeks of cyclosporin A treatment before enrollment.
 - Wash out period of 2 weeks before enrollment.
8. CMV viremia, as defined by positive PCR (≥ 3.5 logarithm) or pp65 test (≥ 5 cells)
9. WHO performance status ≥ 3
10. Pregnant or breast feeding patients^{2,3}
11. Patients with end-stage hepatic, renal or cardiac failure, or any other life-threatening concurrent disease
12. Patients with HIV infection

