7.2.4.1 Baseline (Visit 0)

Refer to the table/flow chart in the appendix 2 for the list of baseline tests.

All patients must provide fully informed written consent before any procedures are done. All baseline tests must be completed within 30 days before registration.

All the tests except for the cataract check up are part of routine clinical care of AA patients, therefore results from tests that are performed no more than 30 days prior to registration can be used to assess the patients eligibility.

The following tests will be performed at the baseline visit in all patients.

- Medical history, including all concomitant diseases
- Review diagnosis of aplastic anemia, including subclassification
- Physical examination, including review of systems
- Review of signs and symptoms of AA (including infections)
- Hematology (WBC with complete differential, platelets, reticulocytes, hemoglobin) within 2 week prior enrollment
- Past history of packed red blood cells (PRBC) and platelet transfusions
- Bone marrow aspirate, including:
 - Cytology study
 - Flow cytometry study
 - Karyotype study (centralized)
 - Molecular studies (for research purpose only: sample to be centralized)
- Bone marrow trephine biopsy
- Peripheral blood immunophenotyping looking for:
 - Expression of glycosylphosphatidylinositol anchored proteins for screening of a PNH clone on erythrocytes, neutrophils, monocytes and lymphocytes
 - Analysis of lymphocyte subsets (CD3+, CD4+, CD8+, CD56+, CD19+)
 - Additional immunologic studies including study of activation and effector markers (Th1/Tc1, Th2/Tc2, Th17, Tregs, T naïve, T central memory, T effector memory, T effector) (for research purpose only: sample to be centralized)
- Chromosomal breakage test for all subjects <20 years of age and >20 years of age suspicious for constitutional aplastic anemia (i.e. Fanconi's Anemia or Dyskeratosis Congenita)
- Complete screening for hepatic, cardiac and renal function (including serum creatinine, BUN, bilirubin, LDH, AST, ALT, total proteins, albumin, Na, K)
- Telomere length (centralized)
- Quality of life questionnaire (EORTC QLQ-C30)³

³ The QoL questionnaire will be administered to the patient before the visit, and, according to standard guidelines, it will be filled independently from the treating physician to avoid biased information.

- Review all records to be included in CRF
 - Blood transfusions
 - Clinical infections, including type, duration, treatment and outcome
 - Adverse effects

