9.1.1 Complete response (CR)

Patients will be considered as complete responders (CR) if achieving all the following:

- Following peripheral blood counts:
 - Hemoglobin >10 gr/dL
 - Absolute neutrophils >1.0 x 10⁹/L
 - Platelets >100 x 10⁹/L
- No evidence of clonal evolution (by marrow cytogenetic and flow cytometry, see below 9.5)

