9.6.8 Clonal evolution, PNH and immunosuppression discontinuation

Incidence and time to clonal evolution will be evaluated in a competing risks framework, considering death and SCT before clonal evolution as competing events.

Incidence and time to PNH will be evaluated in a competing risks framework, considering death and SCT before PNH as competing events.

Incidence and time to discontinuation of immunosuppressive therapy will be evaluated in a competing risks framework, considering death and SCT before discontinuation of IS as competing events.

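### FISH is scheduled only from month 3 and Section 9.5 does not require absence at entry, so a clone missed by the baseline karyotype can count as new clonal evolution

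*Protocol*

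**What the plan says.** Section 9.5 sets the cytogenetic follow-up: "Standard karyotype and FISH for chromosomes 7, 8 and 5 will be performed at 3, 6, 12, 18 and 24 months". I found no other mention of FISH in the protocol.

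Section 7.2.4.1 itemises the baseline aspirate as cytology, flow cytometry, "Karyotype study (centralized") and "Molecular studies (for research purpose only: sample to be centralized"). Neither the visit table in Appendix 2 nor the laboratory manual in Appendix 8 adds FISH at baseline.

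The 9.5 definition has three branches: acute leukaemia, MDS, and an isolated abnormality. The third reads "Occurrence of any cytogenetic abnormality (in absence of other criteria qualifying for the diagnosis of MDS) which can be demonstrated in at least 10" per cent of marrow cells, and the finding must be made "in at least two bone marrow specimens drawn with an interval of at least 3 months". No branch mentions comparison with baseline.

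Section 9.6.8 gives the analysis: "Incidence and time to clonal evolution will be evaluated in a competing risks framework, considering death and SCT before clonal evolution as competing events". Clonal evolution is also an event in event-free survival (9.6.6) and a competing event for response and relapse (9.6.2 to 9.6.4, 9.6.7). Its absence is a condition of complete response (9.1.1): "No evidence of clonal evolution (by marrow cytogenetic and flow cytometry, see below 9.5").

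**The concern.** Ascertainment is not like for like. Entry is screened with one cytogenetic test and follow-up with that test plus a second. Adding a test can only increase what is found, so some clones first seen at follow-up may have been there at randomisation. The two-specimen rule shows that a clone persists. It does not show that it is new, because both specimens may come from after entry.

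This matters because Section 2.4.1 and Appendix 5 single out clonal evolution as the long-term safety question for eltrombopag. False events that occur equally in both arms dilute the risk ratio, so a real harm would look smaller. A patient with an unseen chromosome 5 or 7 loss or deletion listed in Appendix 1 would moreover have been excluded under criterion 3 had it been found at entry.

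**Working it through.** **1. Schedule side by side**

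| Time | Karyotype | FISH 5, 7, 8 | Source |
|---|---|---|---|
| Baseline | yes | not listed | 7.2.4.1 |
| Month 3 | yes | yes | 9.5; Appendix 2 limits this marrow to complete responders |
| Months 6, 12, 24 | yes | yes | 9.5, Appendix 2 |
| Month 18 | yes | yes | 9.5; Appendix 2 shows no marrow |

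**2. Can a clone large enough for 9.5 be missed at entry?**

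The protocol gives neither the number of metaphases nor the rule for calling a clone. I assume m metaphases and a call at r abnormal cells, with r = 2 for a gain or structural change and r = 3 for a loss. The chance of a miss is P(X < r), where X is binomial(m, p) and p is the clone's share of cells.

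For m = 20 and p = 0.10:
- r = 2: 0.9^20 + 20 × 0.1 × 0.9^19 = 0.122 + 0.270 = 0.392
- r = 3: add 190 × 0.01 × 0.9^18 = 0.285, giving 0.677

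| Metaphases | 10% clone, r = 2 / r = 3 | 20% clone, r = 2 / r = 3 |
|---|---|---|
| 10 | 0.736 / 0.930 | 0.376 / 0.678 |
| 15 | 0.549 / 0.816 | 0.167 / 0.398 |
| 20 | 0.392 / 0.677 | 0.069 / 0.206 |
| 25 | 0.271 / 0.537 | 0.027 / 0.098 |

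The 10% threshold therefore does not by itself screen out clones that were present but unseen at entry.

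**3. Effect on the comparison (illustration)**

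Let c be the share of patients with a clone at entry that the karyotype missed and that later meets 9.5. Let p be the true 24-month risk. Then observed risk = c + (1 − c)p. Neither c nor p is in the documents; both are assumed.

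True risks 5% v 10% (ratio 2.00, difference 5.0 points):

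| c | Control | Experimental | Ratio | Difference (points) | Spurious share of control events, c / observed |
|---|---|---|---|---|---|
| 1% | 5.95% | 10.90% | 1.83 | 4.95 | 17% |
| 3% | 7.85% | 12.70% | 1.62 | 4.85 | 38% |
| 5% | 9.75% | 14.50% | 1.49 | 4.75 | 51% |

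True risks 10% v 15% (ratio 1.50): the observed ratio is 1.45, 1.38 and 1.33.

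**4. Power in context**

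With n = 100 per arm and a two-sided 5% test, power = Φ{[Δ − 1.96√(2p̄(1 − p̄)/n)] / √([p₁(1 − p₁) + p₂(1 − p₂)]/n)}. For 5% v 10% without misclassification this is Φ{(0.050 − 0.0730)/0.0371} = Φ(−0.62), about 27%. At c = 1%, 3% and 5% it is about 24%, 20% and 18%.

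**5. Event-free survival**

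No response at 6 months is already a failure (9.4, 9.6.6). The 68% six-month response to horse ATG cited in Section 2 implies that about 100 − 68 = 32% of control patients have an event by then. A false clone found in such a patient at month 6 or later adds nothing.

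**The case against.** The strongest reply is that 9.5 is a list of follow-up times. It omits baseline for karyotype as well, yet karyotype is done at baseline, so the sentence does not say that FISH is absent at entry. That is fair, and the inference rests on the itemised list in 7.2.4.1. But that list is where the baseline tests are fixed, and it names the cytogenetic test without FISH. The word for occurrence in the third branch may also be meant as new onset. Without entry FISH, however, newness cannot be checked for a clone that the karyotype missed. An unseen SAP could define new onset, but it cannot supply a test that was not run.

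The filter in 9.5 is real. A reader might infer that a single positive FISH at the first follow-up marrow is an event. For an isolated abnormality such as +8 it is not, because the 10% and two-specimen conditions apply. For −7 or −5 the Appendix 1 exception might be read as waiving the second specimen, but the MDS branch names morphology, flow cytometry and karyotype, not FISH, so this is only one reading.

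A reader might also infer that the primary endpoint is distorted through the clonal condition in complete response. The third branch cannot do this on the scheduled marrows: month 3 is the first follow-up specimen, and a clone missed at baseline supplies no earlier one. Only the −7/−5 reading leaves a route.

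It also stands that follow-up karyotypes can reveal a clone missed by chance at entry, so FISH is not the only source of such events. The comparison has low power in any case under the assumed risks.

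**Conclusion.** The point holds as a gap in ascertainment and definition. Followed as written, the plan looks for clonal evolution with more tests after entry than at entry and does not exclude clones that were already there. Under equal contamination the incidence rises in both arms and the risk ratio moves toward 1, while the risk difference hardly changes.

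The size is unknown. The figures 1.83 to 1.49 rest on an assumed 1% to 5% of patients with such clones and on assumed true risks of 5% and 10%. A stated bias, a material effect on event-free survival, or different numbers of false events by arm would go beyond the documents. What may differ by arm is timing, because the month-3 marrow is taken only in complete responders. This is a worthwhile, inexpensive improvement to one secondary endpoint, which is also the trial's stated long-term safety question.

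**What to change.** - Add baseline to the FISH times in 9.5 and FISH for chromosomes 5, 7 and 8 to the marrow list in 7.2.4.1, run on the marrow drawn for the baseline karyotype.
- Define the cytogenetic branch of 9.5 as an abnormality absent at baseline by the same method. This also settles known entry abnormalities, since Section 6.2 says that "patients with del(20q), +8 and -Y are not included in this category" and so admits these patients, while 9.5 does not set such clones aside.
- Report a sensitivity analysis restricted to karyotype-detected evolution, the one method used both at entry and at follow-up.
- For patients already enrolled, use look-back FISH only where baseline material and consent allow. Section 7.2.4.3 requires a second consent for banked samples, lets minors' samples stay at local sites, and says the samples are not analysed within the trial.

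The cost is one laboratory panel per patient, in most cases on an existing sample. It may not be free of extra procedures everywhere, because the baseline marrow can be a clinical sample taken up to 30 days before registration. The protocol would also have to say how a FISH-only finding at baseline bears on exclusion criterion 3. The sensitivity analysis does not remove clones that the baseline karyotype missed by chance and a later karyotype found.

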13. Patients without social health care assistance
14. Participation in another clinical trial within 1 month before the start of this trial
15. Patients and/or female partners of male patients not using highly effective method of birth control i.e. intrauterine device (IUD), hormonal (oral pill, injection, implants), tubal ligation or partner's vasectomy
16. Patients with known hypersensitivity to any of the component medications

The presence of a Paroxysmal Nocturnal Hemoglobinuria clone **is not** an exclusion criterion.

Hepatitis-AA (HAA) syndrome [34] is not an exclusion criterion; similarly, the evidence of HBV or HCV infection is not an exclusion criterion *per se*, provided that there is no evidence of hepatic failure (see exclusion criterion #11)

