APPENDIX 2 Summary of Evaluation and Visit Schedule

Procedure	Visit 0	Visit 1	Visit 2,3,4,5	Visit 6,7,8	Visit 9	Visit 10,11	Visit 12	Visit 13,14	Visit 15	Visit 16,17	Visit 18	Visit 19	Visit 20	Visit 21	Visit 22
Time	Pre	d0-1	w1,2,3,4	m1.5,2,2.5	m3	m4,5	m6	m7,8	m9	m10,11	m12	m15	m18	M21	m24
Medical history	X														
Diagnosis	X														
Physical examination	X	X	X	X	X	X	X	X	X	X	X	X	X	X	X
Signs and symptoms	X	X	X	X	X	X	X	X	X	X	X	X	X	X	X
Hematology	X	X	X	X	X	X	X	X	X	X	X	X	X	X	X
Transfusion record	X	X	X	X	X	X	X	X	X	X	X	X	X	X	X
Bone Marrow [#]	X*				X [§]		X*				X				X*
Trephine biopsy	X						X				X				X
Immunophenotype	X*						X*				X				X*
DEB test	X [^]														
Biochemistry	X	X	X	X	X	X	X	X	X	X	X	X	X	X	X
Telomeres	X*						X*								X*
QoL	X						X				X				X
Concomitant medications	X	X	X	X	X	X	X	X	X	X	X	X	X	X	X
All record review	X	X	X	X	X	X	X	X	X	X	X	X	X	X	X
HCG	X ^{^^}														
CsA level			X	X	X	X	X	X	X	X	X	X	X	X	X
Treatment Compliance			X	X	X	X	X	X	X	X	X	X	X	X	X
Ophthalmologic function (cataracts)	X				X		X				X	X	X		X
Safety Monitoring	X	X	X	X	X	X	X	X	X	X	X	X	X	X	X

[figure not shown]
*: centralized samples

[§]in the case of CR, at 3 months bone marrow (BM) evaluation is to be performed.

[^]: only in patients <=20y, or with familiar history of AA; ^{^^}: female patients only

[#]additional BM may be performed according to clinical needs and standard practice: clonal evolution implies BM evaluation, by definition.

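### Section 9.5 and Appendix 2 give conflicting marrow schedules for clonal evolution (months 3 and 18), and the cytogenetic criterion does not exclude abnormalities with which patients may enter

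*Protocol*

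**What the plan says.** **Schedule.** Protocol 9.5: "Standard karyotype and FISH for chromosomes 7, 8 and 5 will be performed at 3, 6, 12, 18 and 24 months". No response condition is attached. In the Appendix 2 visit table, the bone marrow row is marked at baseline and at months 3, 6, 12 and 24. The month-3 mark has a footnote: "in the case of CR, at 3 months bone marrow (BM) evaluation is to be performed". The month-18 column has no marrow mark. Another footnote allows unscheduled marrows: "additional BM may be performed according to clinical needs and standard practice: clonal evolution implies BM evaluation, by definition".

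**Event definition.** Clonal evolution under 9.5 is acute leukaemia, MDS, or a third category: "Occurrence of any cytogenetic abnormality (in absence of other criteria qualifying for the diagnosis of MDS"), shown "in at least 10% of bone marrow cells in at least two bone marrow specimens drawn with an interval of at least 3 months". The two-specimen rule belongs to the third category only.

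**Entry.** Section 6.2 excludes karyotypes typical of MDS, but "patients with del(20q), +8 and -Y are not included in this category, and thus are eligible for this study". It also says that "The presence of a Paroxysmal Nocturnal Hemoglobinuria clone" does not exclude a patient.

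**Use.** CR requires no evidence of clonal evolution (9.1.1). Clonal evolution ends EFS (9.6.6) and is a competing event for the response endpoints and relapse (9.6.2 to 9.6.4, 9.6.7). It is also analysed as an endpoint itself, by cumulative incidence, Gray test and cause-specific Cox regression (9.6.8, 12.3). For PNH, "Incidence and time to PNH will be evaluated in a competing risks framework". Section 2.4.1 and Appendix 5 single out clonal evolution as a safety question for eltrombopag.

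**The concern.** Sites cannot follow 9.5 and Appendix 2 together. If they follow Appendix 2, who has a month-3 marrow depends on CR, the outcome that eltrombopag is meant to raise threefold. A complete responder's clone can be confirmed on the month-3 and month-6 marrows. Other patients need months 6 and 12 unless a clinical marrow is taken. Without a month-18 marrow, an abnormality arising after month 12 has one scheduled specimen left, at month 24, so scheduled marrows cannot confirm it within follow-up.

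The second issue is the word 'any' in the third criterion of 9.5. The three abnormalities allowed at entry are not on the Appendix 1 list, so they fall in this category, and the FISH panel targets one of them (chromosome 8). Nothing says that the abnormality must be new. The baseline marrow precedes randomisation (7.2.4.1), so baseline plus month 3 can span the required three months. A patient with CR-level counts could then be refused CR at the primary time point, have EFS ended and count as clonal evolution, with no change in the clone. New PNH populations raise the same question, because baseline clones are allowed.

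**Working it through.** **Plan's own figure.** The protocol gives no incidence, event count or power for clonal evolution. Its CR planning figure (12.1) reproduces. With 7% v 21%, two-sided alpha 0.05 and 80% power, n = [1.96·√(2·0.14·0.86) + 0.842·√(0.07·0.93 + 0.21·0.79)]² / 0.14² = 95.2, so 96 per arm (power 80.3%).

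**Passages side by side.**

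| Month | 9.5 | Appendix 2 |
|---|---|---|
| 3 | all patients | CR only |
| 6, 12 | all | all |
| 18 | all | none |
| 24 | all | all |

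**Month 3.** Expected month-3 marrows per 100 under Appendix 2 are 100 × 0.07 = 7 (control) and 100 × 0.21 = 21 (eltrombopag). Under 9.5 they are 100 in each arm.

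Assumptions: true 24-month incidence F of 5%, 10% or 15%, equal in both arms; constant hazard; onset independent of CR; clones persist; scheduled marrows only. Onset by month t is P(t) = 1 − (1 − F)^(t/24). Under Appendix 2, confirmation by month 6 needs CR and onset by month 3, so it equals CR rate × P(3).

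| F | P(3) | Control | Eltrombopag | Difference (points) |
|---|---|---|---|---|
| 5% | 0.64% | 0.04% | 0.13% | 0.09 |
| 10% | 1.31% | 0.09% | 0.27% | 0.18 |
| 15% | 2.01% | 0.14% | 0.42% | 0.28 |

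By month 12, every clone with onset by month 6 is confirmed in both arms (P(6) = 2.6% at F = 10%), so the difference is gone. An individual responder's lead is 3 months if events are dated at first detection (month 3 v 6), or 6 months if dated at confirmation (month 6 v 12).

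Transient clones give a less favourable case. Assume that 5% carry a clone at months 3 to 6 and half have lost it by month 12. Confirmed incidence is then 0.21·5% + 0.79·2.5% = 3.03% v 0.07·5% + 0.93·2.5% = 2.68%, a difference of 0.35 points.

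**Month 18.** Confirmation by month 24 needs onset by month 12 under Appendix 2, but only by month 18 under 9.5.

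| F | Appendix 2: P(12) | 9.5: P(18) |
|---|---|---|
| 5% | 2.5% | 3.8% |
| 10% | 5.1% | 7.6% |
| 15% | 7.8% | 11.5% |

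The loss is the same in both arms.

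**Baseline abnormalities counted.** With prevalence b at entry (assumed 1% to 10%), the observed risk is b + (1 − b)p. Take a true 5% v 10% (assumed: ratio 2.0, power 26.7% at 100 per arm).

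| b | Observed | Ratio | Difference (points) | Power |
|---|---|---|---|---|
| 1% | 5.95% v 10.9% | 1.83 | 4.95 | 24.1% |
| 5% | 9.75% v 14.5% | 1.49 | 4.75 | 17.5% |
| 10% | 14.5% v 19.0% | 1.31 | 4.5 | 13.4% |

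**Primary endpoint.** If such patients are refused CR, the loss per 100 at b = 5% is 7 × 0.05 = 0.35 (control) and 21 × 0.05 = 1.05 (eltrombopag). Power at 96 per arm falls from 80.3% to 77.9% (79.8% at b = 1%, 75.3% at b = 10%).

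**The case against.** A reader might infer that the protocol looks for clones at month 3 only in complete responders, and so distorts the arm comparison. The documents do not support that. Section 9.5 says the opposite, and nothing settles which passage governs. Under 9.5, scheduled surveillance does not depend on arm. Under Appendix 2 the effect is a fraction of a percentage point, Appendix 2 allows marrows on clinical need, and leukaemia and MDS (including Appendix 1 karyotypes) need no second specimen. This stands.

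A reader might also infer that the plan definitely counts baseline clones and that this favours one arm. Neither follows. 'Occurrence', 'evolution' and 'incidence' can all be read as meaning new, and baseline karyotype is collected, so entry clones can be identified. Randomisation spreads them evenly, and the absolute difference hardly moves (5.0 to 4.75 points at b = 5%). What remains is that two careful readers could classify the same patient differently, in a definition that also feeds CR and EFS. An analysis plan might settle this, but the open wording is in the protocol definition itself.

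Finally, a reader might want all PNH outcomes limited to patients without a baseline clone. That goes too far. The protocol separates PNH population occurrence from clinical hemolytic PNH, and a patient entering with a clone can still newly develop hemolysis.

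**Conclusion.** Two points hold. First, 9.5 and Appendix 2 contradict each other at months 3 and 18; this is certain from the text. If Appendix 2 is followed, the dependence on response is real but small: about 0.1 to 0.3 points at month 6 for an assumed 5% to 15% incidence, nil by month 12 if clones persist, and 0.35 points in the transient-clone example. The month-18 gap is larger, about 1.2 to 3.7 points of unconfirmed events over the same range, but equal in both arms.

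Second, read literally, 9.5 counts an eligible baseline abnormality as an event. That dilutes the ratio, costs some power for clonal evolution and can remove a few complete responses from the primary endpoint, without favouring an arm. Its size rests on an entry prevalence that the protocol does not give. Neither point shows that the arm comparison is distorted. Both should be corrected, because clonal evolution is the safety question that the protocol itself stresses.

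**What to change.** 1. Reconcile 9.5 with Appendix 2 at months 3 and 18, so that scheduled ascertainment does not depend on response. Which marrows are taken is for the trial's clinicians to decide.
2. If sites follow Appendix 2, add a sensitivity comparison using cytogenetics from the marrows scheduled for all patients (months 6, 12 and 24). Keep AML, MDS and clinically driven findings in the main safety comparison. State that scheduled marrows cannot confirm a clone arising after month 12 within 24 months.
3. In the third criterion of 9.5, count only abnormalities absent at baseline, or new ones in addition to a baseline abnormality. Report baseline abnormalities separately by arm. Apply the same definition to CR (9.1.1) and EFS (9.6.6).
4. Analyse new PNH populations in patients without a baseline clone. Keep clinical hemolytic PNH as an endpoint for every patient without it at baseline.

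Items 2 to 4 cost protocol wording and one sensitivity analysis, with no extra procedures. Item 1 costs wording only if the schedule is aligned to what sites already do; otherwise it adds marrows at months 3 or 18.
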